## **2 JUSTIFICATION**

BCG is rarely given at birth in rural areas in low-income countries; in rural Guinea-Bissau only 38% are vaccinated with BCG in the first month of life. A major reason for this delay is the immunization programme (EPI)'s focus on reducing wastage of vaccines. Freeze dried vaccines like BCG have to be used within 6 hours after reconstitution with a diluent. Therefore, a vial of BCG vaccine, which contains 20 doses, is not opened unless 10-12 children are present to be vaccinated. Hence, there are many missed vaccination opportunities. This delay in BCG vaccination may be very important. Approximately 75% of neonatal deaths occur within the first week of life and only 11% of the children receive BCG in the first week of life. If BCG vaccine indeed has profound effects on innate immunity and neonatal mortality and morbidity in both LBW and NBW children many lives could be saved if BCG was provided earlier.

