## **5.5 Outcomes**

### 5.5.1 Primary outcome: Non-accidental early infant mortality

The primary outcome is non-accidental mortality between the home visit and, the next follow-up visit by the BHP, when all unvaccinated children, who are home will be offered BCG or the date, where the first non-trial vaccine is registered by BHP. All children living in intervention and control clusters will be followed through the rural or urban HDSS routines, where information on vital

status of all followed children is collected. With declining mortality, we may however not be able to obtain conclusive result. We have therefore defined the sample size for the composite outcome, but retained mortality as the primary outcome.

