#### 5.7.4 Primary analyses of secondary outcomes

We will assess the effect of BCG and OPV on severe morbidity (hospital admission and composite outcome of hospital admission and death) using Cox proportional hazards models with age as underlying time scale. We will furthermore assess the effect of BCG and OPV on the above-mentioned other secondary outcomes. The effect on growth measures will be assessed in linear regression models. To assess the effect on BCG scarring and consultations, we will use binary regression models.

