Outline stata code: For analysis For model checking	<pre> stset outdate, f(event==1) enter (max(dob+1, date_enrol) /// exit (min (dnasc+60, date_mobileteam) origin(dob) stcox random, strata(sex reg prmorlev) vce(cl regam) estat phtest, detail† stphplot, strata(random) adj(sex reg prmorlev) stcox random, strata(sex reg prmorlev) vce(cl regam) tvc(random) texp(_t) *reg=region, prmorlev=pre-study mortality level, regam=village cluster </pre>

† If the proportional hazards assumption is not fulfilled we will still report the marginal hazard ratio but it will be supplemented by hazard ratios for two-three categorized time periods.

Table 9: All-cause consultations

Population	Identical to primary analysis of primary outcome
Observation period	From: Enrolment visit or 24 hours after birth, whichever comes last To: 60 days of life Censoring, first of: 
 - Visit by the BHP - Date of registering first non-trial vaccine given after enrolment - 60 days

	
 - Migration (migration out of the study area as per HDSS definition) - Death - End of study
Failure definition	An out-patient consultation within the observation period
Statistical tool	Log-binomial regression
Adjustment	We will adjust the analysis for sex, region and pre-study mortality level
Clustering	We will use robust standard errors to account for clustering within village cluster
Stata code	Binreg cons random sex b1.reg pmorlev, rr vce(cl regam) *cons=out-patient consultation, reg=Region, pmorlev=Pre-study mortality level, regam=village cluster

Growth

Table 10: Mid-upper-arm circumference (MUAC)

Population	Identical to primary analysis of primary outcome
Observation time point	First visit by the mobile teams
Growth measures	MUAC will be analysed using the measured value
Statistical tool	Linear regression
Adjustment	We will adjust the analysis for MUAC at enrolment, age at MUAC measurement, sex, region and pre-study mortality level
Clustering	We will use robust standard errors to account for clustering within village cluster
Stata code	Regress MUAC random sex b1.reg pmorlev MUACenrol MUACage, /// vce(cl regam) *reg=region, pmorlev=pre-study mortality level, MUACenrol=MUAC at enrolment, MUACage= age at MUAC assessment, regam=village cluster

Table 11: Weight-for-age z-score

Population	Identical to primary analysis of primary outcome
Observation time point	First visit by the mobile teams

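### Consultations (SAP Table 9) are analysed as a yes/no risk ratio over unequal observation windows with no person-time term; if health-centre BCG or OPV in control children closes the window, the risk ratio exceeds 1 under no effect

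*SAP*

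**What the plan says.** SAP Appendix 2, Table 9 starts each child's window at the later of the enrolment visit and 24 hours of age. The limit is "To: 60 days of life". The window closes sooner at a BHP visit, migration, death, end of study, or the "Date of registering first non-trial vaccine given after enrolment". The outcome is "An out-patient consultation within the observation period" and the tool is "Log-binomial regression". The code line is "Binreg cons random sex b1.reg pmorlev, rr vce(cl regam"); its terms are arm, sex, region and pre-study mortality level, with no offset and no time variable. Protocol 5.7.4 is consistent with this: "To assess the effect on BCG scarring and consultations, we will use binary regression models".

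Tables 7 and 8 (hospital admission, severe morbidity) have nearly the same windows but use Cox models with age as the time scale.

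Neither document defines *non-trial vaccine*. Protocol 5.5.1 words the rule for the primary outcome as "the date, where the first non-trial vaccine is registered by BHP". The hypothesis in Protocol section 4 mentions only the next home visit or pentavalent vaccine.

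**The concern.** A yes/no model cannot censor. A child observed for 3 days and one observed for 58 days weigh the same if neither consulted. That does no harm under no effect when window lengths have the same distribution in both arms. It produces a bias when they do not.

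The plan makes a difference between arms plausible. Control children get no vaccine at the home visit and are told they can be vaccinated at the health centre (Protocol 5.4.2). Intervention children have had BCG and OPV, and their next scheduled vaccines fall at 6 weeks (Protocol 1.1). BCG from a health centre is not given by the trial and is given after enrolment, so it fits Table 9's wording. If it closes the window, control children have less time in which to be counted as consulting.

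Protocol 8.3 and the SAP name consultations as one route for capturing other serious adverse events. The SAP's cost-effectiveness paragraph takes different consultation rates into account, and Table 9 does not yield a rate. An artefactual excess in the intervention arm could be read as harm or extra cost.

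**Working it through.** The documents give no figure for consultations, so there is nothing to reproduce first.

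**Inputs from the documents**
- BCG uptake: 11% in the first week ("only 11% of the children receive BCG in the first week of life") and 38% in the first month in rural Guinea-Bissau (Protocol section 2).
- Rural visits every two months (Protocol 5.1.1); urban follow-up at 2 months (Protocol 5.4.3.2).
- Pentavalent vaccine from 6 weeks (Protocol 1.1).

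**Assumptions**
- Entry uniform over days 1 to 3 (mean 2).
- Rural visit age uniform over 0 to 60 days; urban visit at day 60.
- 30% of children in both arms get pentavalent vaccine, spread evenly over days 42 to 60.
- Rural BCG uptake applies in the urban area, evenly spread within days 2 to 7 and 7 to 30.
- The same constant consultation rate in both arms, giving 10%, 20% or 40% risk over the full period.

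**Formula.** With rate λ and window W, the risk in an arm is E[1 − exp(−λW)], which is close to λ·E[W] when consultations are uncommon. The risk ratio under no effect is therefore close to the ratio of mean windows, intervention over control.

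**Urban timing, no BCG uptake after day 30**
- Intervention: 60 − 2 − 0.30 × 9 = 55.3 days.
- Control: 0.62 × 55.3 + 0.11 × 2.5 + 0.27 × 16.5 = 34.29 + 0.28 + 4.46 = 39.0 days. Here 2.5 and 16.5 are the mean days from entry to BCG in the two uptake periods.
- Ratio: 55.3 / 39.0 = 1.42.

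**Rural timing, no BCG uptake after day 30**
- Intervention: 58/2 − 0.30 × 108/116 = 29 − 0.28 = 28.7 days.
- Control: a child given BCG s days after entry contributes on average s − s²/116 days, because the visit may come first. This averages 2.43 days for the first-week group and 13.77 for the later group. The mean is 0.62 × 28.7 + 0.11 × 2.43 + 0.27 × 13.77 = 17.79 + 0.27 + 3.72 = 21.8 days.
- Ratio: 28.7 / 21.8 = 1.32.

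**Simulation under no effect, 1,000,000 children per arm**

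| BCG uptake in controls | Rural: mean days, control / intervention | Rural risk ratio | Urban: mean days, control / intervention | Urban risk ratio |
|---|---|---|---|---|
| 11% day 7, 38% day 30, none later | 21.8 / 28.7 | 1.29–1.32 | 39.0 / 55.3 | 1.39–1.42 |
| Same, rising to 60% by day 60 (assumed) | 21.3 / 28.7 | 1.32–1.35 | 36.2 / 55.3 | 1.47–1.51 |
| About half: 5%, 19%, 30% by day 60 | 25.1 / 28.7 | 1.14 | 45.8 / 55.3 | 1.19–1.20 |
| BCG does not close the window | 28.7 / 28.7 | 0.99–1.00 | 55.3 / 55.3 | 0.99–1.00 |

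Events divided by person-time in the same data gave 0.99 to 1.01 in every row.

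**If vaccination contacts are recorded as consultations** (rural, 20% rate, first row). Risks are 0.078 in controls and 0.103 in the intervention arm, and 30% of control windows close at BCG. If a share q of those contacts is also recorded as a consultation, control risk is about 0.078 + 0.30q.
- q = 5%: 0.103 / 0.093 = 1.11.
- q = 10%: 0.103 / 0.108 = 0.95 (simulated 0.96).
- q = 20%: 0.103 / 0.138 = 0.75 (simulated 0.76).
- The ratio crosses 1 near q = 0.025 / 0.30, about 8%.

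**The case against.** The strongest reply is that the shorter control window is inferred. BCG and OPV are the trial's own vaccines, so *non-trial* may mean pentavalent and later vaccines only. The hypothesis names pentavalent vaccine, and OPV campaigns are censored only in a sensitivity analysis. Alternatively, a vaccine registered by BHP may count only from BHP's own visit. On either reading the windows are equal and the arm bias is gone. This stands as a condition on the result. It does not displace the plain reading: Table 9 lists the BHP visit and the vaccine date as separate events, so the vaccine entry would be redundant if it took effect only at that visit. The pentavalent wording is in the hypothesis, not in the censoring rule.

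A reader might infer that the trial will report a spurious increase in consultations. The documents do not support that. Besides the undefined term, they do not say whether a visit for vaccination can be recorded as a consultation, and a modest share of such records would reverse the direction.

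The size is also uncertain. The 38% is a rural figure, and the Protocol does not say whether it includes BCG given by BHP nurses, whose visit already closes the window. The half-uptake row covers part of that doubt.

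A reader might also count early deaths, scored as no consultation, as a material flaw. Protocol 5.3 expects deaths and admissions together in only 2.4% of children, and a child who consulted before dying still counts as an event.

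**Conclusion.** Table 9's model does not match its observation period. That holds on any reading, because the model has no person-time term while Tables 7 and 8 use Cox models on nearly the same windows. Whether this biases the comparison between arms depends on coding rules the plan leaves open.

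If health-centre BCG or OPV closes a control child's window when given, the risk ratio under no effect is about 1.3 with rural visit timing and 1.4 to 1.5 with urban timing. At half the uptake it is about 1.1 to 1.2. These figures assume rural uptake in the urban area, and assume uptake after day 30, pentavalent timing, visit ages and consultation rates. If only pentavalent or later vaccines count, or vaccines take effect only at the BHP visit, the arm bias is nil.

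SAP Appendix 1 sets no significance threshold for secondary outcomes and rests the main conclusion on the primary analysis, so that conclusion is unaffected. Safety capture and cost-effectiveness are reason enough to correct the table before analysis. Confidence is moderate.

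**What to change.** 1. Replace the log-binomial model in Table 9 with time to first consultation, using the Cox model of Tables 7 and 8: the same stset with consultation as the failure, the same strata and the same cluster-robust variance. Applying Table 9's censoring already requires consultation dates.
2. Define *non-trial vaccine*, stating whether BCG and OPV given outside the trial count, and whether the date given or the date recorded applies.
3. Exclude contacts made only for vaccination from the consultation outcome.

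Protocol 5.5.2 describes a timing questionnaire for admissions only. If consultation dates were not recorded, keep the yes/no outcome but end the window at the BHP visit in both arms regardless of vaccination. Fit a complementary log-log model with log(days to that visit) as offset and cluster-robust variance. Do not use vaccine-censored days as the offset. Undated consultations would be counted up to the interview, and the shorter control denominator would give a rate ratio under no effect of about 21.8 / 28.7 = 0.76 (rural) or 39.0 / 55.3 = 0.71 (urban).

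Cost: one SAP table and two definitions, with no new data for the undated version. The estimate becomes a hazard ratio instead of a risk ratio. The undated version includes some control follow-up after BCG, which dilutes the contrast.

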## **Study site**

55 rural clusters followed through Bandim Health Project's Rural Health and Demographic Surveillance site in Oio, Biombo and Cacheu regions in Guinea-Bissau and 37 urban clusters followed through Bandim Health Project's Urban Health and Demographic System site in Bissau.

Bandim Health Project, [name], Guinea-Bissau

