## Protocol changes

- May 2015     Original protocol (*Approved by the Guinean ethical committee June 2015*)
- May 2016     Protocol adapted to include Tokyo 172 strain from BCG Japan (*Approved by the Guinean ethical committee June 2016*)
- May 2017     Definitions of primary and secondary outcomes were clarified. Analyses section was clarified and supplemented by the analysis plan. Sample size considerations were updated.
- The Danish BCG strain was removed from the protocol, since this strain was only used during the pilot phase of the trial.
- June 2017     Study area was expanded to include BHP's urban study area. The protocol format was changed to comply with the current guidelines of the Ethical Committee in Guinea-Bissau.

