#### 5.1.1 The rural HDSS

The rural HDSS was established in 1990. The BHP teams survey women of fertile age and their children below the age of 5 years in randomly selected clusters of villages in all the nine health regions in the country. Children in the three rural regions closest to Bissau (Oio, Biombo and Cacheu) will be eligible for the study.

The rural clusters are followed with two-monthly visits by the mobile teams. At all visits the women are asked whether they are pregnant. When a pregnancy is registered; the woman's nutritional status is assessed by measurement of a mid-upper-arm-circumference (MUAC); information on antenatal care is collected prior to giving birth, as well as at the first visit after delivery. Socio-economic factors (type of roofing, type of bathroom, possession of a mobile phone, radio and generator) are registered. After the delivery, information on the place of delivery (home, health facility) and who assisted the delivery is collected.

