#### 5.1.2 The urban HDSS

The urban HDSS was established in 1978. Fieldwork assistants follow children below the age of 3 years through home visits every third month. Pregnancies are registered every month and followed monthly until birth. When a pregnancy is registered information on ethnic group, gestational age, use of mosquito net is collected. After the delivery, information on place of delivery (home, health facility) is collected. Children in the urban study area will be eligible for the study.

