#### *5.4.3.2 Follow-up in the urban region*

The study participants will receive two follow-up visits by the study nurse at 2 and 4 months of age. The study nurse will bring BCG and OPV for children in control clusters. For the remaining routine vaccines as part of the national programme, the children will be referred to the closest health care centre. All children below the age of 3 years are followed through home visits every third month, where information on vital status, breastfeeding status, supplementary feeding, MUAC, vaccinations, hospital admissions and vaccination campaigns are collected.

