#### 5.7.3 Primary analysis of the primary outcome

In the primary analysis of the primary outcome, we will compare the effect of BCG and OPV on early infant mortality in a Cox proportional hazards model with age as underlying time. The analysis will be performed on a per-protocol population consisting of all BCG-unvaccinated children visited within 72 hours after birth, who received the assigned treatment. Follow-up will be censored at:

- Subsequent visit by the BHP in rural areas or follow-up visits by the study nurse in the urban area, where children in the control group will receive BCG
- Date of registration of first non-trial vaccine
- Death due to accident
- Migration

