Statistical tool	Cox proportional hazards model
Stratification	We will employ models that allow for different baseline hazards according to sex, region and pre-study mortality level
Clustering	We will use robust standard errors to account for clustering within village cluster
Outline stata code For analysis: For model checking:	<pre> stset outdate, f(dead==1) enter (max(dob+1, date_enrol) /// exit (min (dnasc+60, date_mobileteam) origin(dob) stcox random, strata(sex reg prmorlev) vce(cl regam) estat phtest, detail† stphplot, strata(random) adj(sex reg prmorlev) stcox random, strata(sex reg prmorlev) vce(cl regam) tvc(random) texp(_t) *reg=region, prmorlev=pre-study mortality level, regam=village cluster </pre>

† If the proportional hazards assumption is not fulfilled we will still report the marginal hazard ratio but it will be supplemented by hazard ratios for two-three categorized time periods.

3 Effect-modifier analyses of primary outcome

We will assess whether the effect of the intervention on the primary effect measure is modified by the following potential effect modifiers.

Table 3. Sex as a potential effect modifier of the primary outcome

Potential effect modifier	Sex
Design	We will perform the analysis as describe above (for the primary analysis) allowing the effect of the intervention to differ between the sexes.
Reasoning	Previous studies have found sex-differential non-specific effects ^{1 2} , therefore, we will assess the sex-differential effects.
Outline stata code: For analysis: For model checking:	<pre>stcox random#sex sex, strata(sex reg pmorlev) vce(cl regam) contrast random#sex estat phtest, detail† stphplot, strata(random_sex) adj(sex reg pmorlev) stcox random#sex sex, strata(sex reg pmorlev) vce(cl regam) /// tvc(random#sex sex) texp(_t) *reg=region, pmorlev=pre-study mortality level, regam=village cluster, random_sex=a four-level variable based on the four possible combinations of random and sex</pre>

† If the proportional hazards assumption is not fulfilled we will still report the marginal hazard ratio but it will be supplemented by hazard ratios for two-three categorized time periods.

Table 4. Maternal BCG scar as a potential effect modifier of the primary outcome

Potential effect modifier	Maternal BCG scar (yes/no)
Design	We will perform the analysis as described above (for the primary analysis) allowing the effect of the intervention to differ by maternal BCG-scar status

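### The SAP is incompletely adapted to the urban area: growth is measured at a mobile-team visit that only rural children receive, and the outline Cox code ends follow-up on the same rural date

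*SAP*

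**What the plan says.** The trial has 55 rural clusters and "37 urban clusters followed through Bandim Health Project's Urban Health and Demographic System site in Bissau" (protocol, Study site). The urban area was added by the June 2017 change: "Study area was expanded to include BHP's urban study area".

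Who visits whom is set out in the protocol:
- Section 5.1.1, rural: "The rural clusters are followed with two-monthly visits by the mobile teams".
- Section 5.1.2, urban routine surveillance: "Fieldwork assistants follow children below the age of 3 years through home visits every third month".
- Section 5.4.3.2, urban trial follow-up: "The study participants will receive two follow-up visits by the study nurse at 2 and 4 months of age". The nurse brings BCG and OPV for control children.

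For censoring, protocol 5.7.3 gives two events: the next BHP visit in rural areas, or "follow-up visits by the study nurse in the urban area".

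In SAP Appendix 2, Tables 10 (MUAC) and 11 (weight-for-age) fix the time point at the "First visit by the mobile teams", and the variable legend under Table 11 repeats it. Both tables define their population as that of the primary analysis. Tables 2, 7, 8, 9 and 13 censor at a BHP visit without saying which kind. The outline code in the four Cox tables (2, 7, 8 and 13) ends follow-up with "exit (min (dnasc+60, date_mobileteam) origin(dob". SAP Appendix 1 makes every analysis complete-case.

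**The concern.** A visit that exists only in the rural area cannot supply an outcome for urban children. An analyst who follows Tables 10 and 11 as written has no urban growth value, and the complete-case rule then removes those children. The results would describe rural children only, under a population statement that says otherwise. An analyst who departs from the wording must choose the urban visit with no prespecified rule.

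Censoring has a related but weaker problem. The only visit date named in the code is the mobile-team date. The SAP's general phrase does not separate the two kinds of urban BHP visit: the nurse's follow-up visit, where controls are offered vaccine, and the three-monthly surveillance visit. The primary outcome depends on ending follow-up when controls are offered BCG, so the rule should name the visit where that happens.

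**Working it through.** **1. Growth: the specifications side by side**

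| Item | Rural | Urban |
|---|---|---|
| Mobile-team visit (protocol 5.1.1) | Every two months | None described |
| Trial follow-up visit (5.4.3) | BHP nurse with the mobile team | Study nurse at 2 and 4 months |
| Routine surveillance (5.1) | Same mobile-team visit | Fieldwork assistant every third month |
| Growth time point (SAP Tables 10, 11) | Defined | Not defined |

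The time point is part of the specification itself, so it cannot be set aside as shorthand in outline code.

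**2. Share of clusters affected**

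37 / (55 + 37) = 37/92 = 40.2% of clusters. This is not a share of children. The documents give no urban share, and protocol section 6 starts urban enrolment in July 2017, a year after the rural scale-up.

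**3. Loss of precision if urban children drop out**

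Assume an urban share u of children, with the same outcome variance and design effect in both areas. The standard error is multiplied by 1/√(1 − u). A comparison with 80% power in the full sample (two-sided 5%) keeps power Φ((1.960 + 0.842)·√(1 − u) − 1.960).

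| Assumed u | SE factor | Power left from 80% |
|---|---|---|
| 10% | 1.05 | 76% |
| 20% | 1.12 | 71% |
| 30% | 1.20 | 65% |
| 40.2% (37/92) | 1.29 | 58% |
| 50% | 1.41 | 51% |

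The plan states no power for growth, so 80% is only a reference point. The SAP sets no significance threshold for secondary outcomes, so the SE column is the more relevant one.

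**4. Bias**

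Protocol 5.2 stratifies randomisation by region. A rural-only comparison therefore still compares randomised clusters within strata. What is lost is coverage of the urban area and precision.

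**5. Primary outcome**

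SAP Table 2 stops follow-up at 60 days. Two months is 2 × 365.25/12 = 60.9 days, so the first urban nurse visit is planned at about the same day. If `date_mobileteam` is missing for urban children, and assuming Stata's `min()` ignores missing values, the exit is day 60. Code and protocol 5.7.3 then differ only for urban nurse visits made before day 60.

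**The case against.** The strongest objection concerns the primary outcome. The SAP is an appendix to the protocol, so the two are read together. Protocol 5.5.1 identifies the relevant visit as the one at which unvaccinated children are offered BCG, and 5.7.3 names the urban study nurse. That nurse is employed by the BHP (5.1.3), so a BHP visit does cover the nurse's visit. The code is labelled an outline. Its exit clause also omits migration and non-trial vaccines, which Table 2 lists, so the undefined `outdate` presumably carries further dates. All of this stands, and it reduces the censoring point to a need for exact wording.

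Three stronger readings are tempting, and the documents do not support them.
- **Urban follow-up is cut by a third.** If three-monthly surveillance visits censored, and the first fell uniformly over 90 days, 60/90 = two thirds of urban children would be censored before day 60, and mean follow-up would fall from 60 to 60 − 60²/180 = 40 days. Protocol 5.7.3 excludes that reading, and it cannot hold together with a missing mobile-team date, which leaves exit at day 60. The figure also ignores censoring at the first non-trial vaccine. Pentavalent vaccine is due at 6 weeks; from 42 days the mean would be 42 − 42²/180 = 32 days, a loss of about 10 days and not 20.
- **The SAP was never updated after the expansion.** It cites a 2018 paper, and Table 2 limits one exclusion to rural villages. Incomplete adaptation is as much as can be said.
- **Urban growth data do not exist.** Protocol 5.4.3.2 has MUAC collected at urban surveillance visits, and protocol Table 1 schedules weighing at the first routine visit without restricting it to rural children. What is missing is the rule for which visit to use.

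It is also fair that growth is a secondary outcome, examined for its pattern. That limits the consequence but does not supply the missing time point.

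**Conclusion.** The point holds for growth. Followed as written, Tables 10 and 11 leave all children in 37 of 92 clusters without a MUAC or weight-for-age outcome, while claiming the full primary-analysis population. The cost in precision depends on the urban share of children, which is not given: an SE factor of 1.05 at 10%, rising to 1.41 at 50%, under equal variance and design effect. No bias follows.

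For censoring, the SAP and its outline code are less specific than protocol 5.7.3 and should be brought into line with it. The effect on the primary outcome is probably small, given the 60-day limit and urban nurse visits held near their planned date.

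**What to change.** - Define one derived first-follow-up date: the first BHP mobile-team visit for rural children, and the first study-nurse follow-up visit for urban children, as in protocol 5.7.3.
- Use it in place of `date_mobileteam` in the code, and in place of the general BHP visit in Tables 2, 7, 8, 9 and 13. State that routine urban surveillance visits do not censor.
- In Tables 10 and 11, take urban growth from the first urban follow-up visit at which the measurement is already recorded, and name that visit separately for MUAC and for weight. Protocol 5.4.3.2 places urban MUAC at surveillance visits; protocol Table 1 places weighing at the first routine visit.
- Keep the adjustment for age at measurement in the MUAC model. Adding age to the weight model is optional, because the z-score is already standardised for age.

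The cost is SAP wording and one derived variable. Age at measurement will spread somewhat more between areas, which the MUAC age term and the weight z-score handle. Some urban MUAC values from surveillance visits may also fall after the 2-month nurse visit, when controls have been offered BCG; the SAP should say whether those are kept.
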